11.3 Source Data

Source documents containing source data provide evidence for the existence of the subject and substantiate the integrity of the data collected. Source documents are filed at the investigator's site.

A separate origin of source data list will be generated before the start of enrolment, specifying the location of the source of derived information appearing in the eCRF. This document must be signed by the PI and the Monitor to confirm agreement before start of recruitment.

Source documents are all documents used by the investigator or hospital that relate to the subject's medical history, and that verify the existence of the subject, the inclusion and exclusion criteria, and all records covering the subject's participation in the trial. They include laboratory

Clinical Trial Protocol

Vicore Pharma AB Version: 2.0 Trial ID: VP-C21-013 Date: 03-MAR-2023

notes, memoranda, material dispensing records, subject files, etc. The eCRF may constitute source data if clearly defined in the origin of source data list.

The investigator must guarantee access to source documents to the monitor, CAs and the IECs, if required.

The monitor will perform ongoing source data verification to confirm that data recorded in the eCRF by authorized site personnel are accurate, complete, and verifiable from source documents; that the safety and rights of subjects are being protected; and that the trial is being conducted in accordance with the currently approved protocol and any other trial agreements, ICH GCP, and all applicable regulatory requirements.

The level of source data verification will be described in the monitoring plan.

11.4 Coding of Data

Medical history and AEs will be coded using the lastest version of Medical Dictionary for Regulatory Activities (MedDRA).

Concomitant medication will be coded using the latest version of World Health Organisation (WHO) Drug Reference List.

11.5 Subject Confidentiality

The confidentiality of the subject data and subject records shall be protected, respecting the privacy and confidentiality rules in accordance with applicable regulatory requirements.

Clinical Trial Protocol

Vicore Pharma AB Version: 2.0 Trial ID: VP-C21-013 Date: 03-MAR-2023

12 RETENTION OF DOCUMENTS

The monitor will instruct the investigator to maintain source documents and the signed informed consent form for each subject.

Furthermore, the monitor will instruct the investigator to archive essential documents for the duration defined in the ICH GCP R2 or for 15 years, whichever comes first.

The sponsor will notify the investigator when retention of the trial-related records is no longer required.

Clinical Trial Protocol

Vicore Pharma AB Version: 2.0 Trial ID: VP-C21-013 Date: 03-MAR-2023

13 STATISTICAL METHODS

The principal features of the statistical analysis to be performed are described in this section. A more technical and detailed elaboration of the principal features will be presented in a separate Statistical Analysis Plan (SAP), which will be signed and approved prior to database lock.

13.1 General

Continuous data will be presented in terms of evaluable and missing observations, arithmetic mean, standard deviation (SD), median, minimum, and maximum value.

Categorical data will be presented as counts and percentages. When applicable, summary data will be presented by treatment, and by assessment time. Individual subject data will be listed by subject number, treatment and, where applicable, by assessment time.

All descriptive summaries and statistical analyses will be performed using SAS Version 9.4 or later (SAS Institute, Inc., Cary, NC).

Baseline (apart from EndoPAT assessments) will be defined as the last non-missing data collection point prior to the (first) administration of IMP. All hypothesis testing will use a significance level of 5 %. No imputation of missing data will be performed.

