6.2 Number of Subjects

The trial will include 10 to 14 randomised subjects, with 12 being the target number.

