13.2 Determination of Sample Size

No formal sample size calculation has been performed for this trial. The proposed sample size is considered sufficient to provide adequate information to meet the trial objectives.

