13.5.1 Analysis of Primary Endpoint

The percentage change in the primary endpoint (RHI) will be compared between treatments using an analysis of variance model (ANOVA) adjusting for subject (random), period and treatment. The adjusted mean difference will be presented together with 90% confidence interval and associated two-sided p-value.

All data will be listed by subject.

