13.5.2 Analysis of Secondary/Exploratory Endpoint

The secondary endpoint (AI) will be compared between treatments using similar ANOVA model as for the primary endpoint.

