13.5.3 Statistical/Analytical Issues

All tests will be two-sided at a 10% significance level. There will be no adjustment for multiple tests.

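### The protocol sets 5% in Section 13.1 and two-sided 10% in Section 13.5.3 for the same tests, so a primary p-value between 0.05 and 0.10 is both significant and not significant

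*Combined protocol and SAP*

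**What the plan says.** Three statements in the protocol's statistical section bear on the significance level.

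- Section 13.1 (General): "All hypothesis testing will use a significance level of 5" per cent. The sentence does not say whether this is one-sided or two-sided.
- Section 13.5.3 (Statistical/Analytical Issues, under Pharmacodynamic Analysis): "All tests will be two-sided at a 10% significance level". It continues: "There will be no adjustment for multiple tests".
- Section 13.5.1 (Analysis of Primary Endpoint): "The adjusted mean difference will be presented together with 90% confidence interval and associated two-sided p-value".

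The tests concerned are the RHI comparison, where the percentage change "will be compared between treatments using an analysis of variance model (ANOVA) adjusting for subject (random), period and treatment" (Section 13.5.1), and the augmentation index (AI) comparison, which uses a similar model with no level of its own (Section 13.5.2). Section 13.5.3.2 adds possible subgroup comparisons and leaves the detail to the SAP. Section 13.6 describes only summaries and listings for safety.

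On size, Section 6.2 says: "The trial will include 10 to 14 randomised subjects, with 12 being the target number". Section 13.2 says: "No formal sample size calculation has been performed for this trial".

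**The concern.** Both level statements are worded to cover every test, and they differ by a factor of two. Giving each its own domain does not reconcile them. If Section 13.5.3 governs the pharmacodynamic comparisons, the available text describes no other test to which the 5% rule could apply.

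What is at stake is the threshold for calling the primary result significant. For a p-value between 0.05 and 0.10, two analysts who both follow the protocol would report opposite conclusions. If the conflict survives into reporting, the level can be picked with the p-value in view. The false-positive rate behind a claim of significance would then be unclear. The protocol commits to publishing the results whatever their direction (Section 18.3), so the label will be used outside the sponsor.

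**Working it through.** **1. Which level does the interval imply?** A 90% interval corresponds to a two-sided level of 1 − 0.90 = 0.10. This agrees with Section 13.5.3 and not with a two-sided 5% in Section 13.1.

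**2. Would a one-sided reading of Section 13.1 reconcile them?** A one-sided 5% test has the same critical value as a two-sided 10% test. However, the documents nowhere say one-sided, and Sections 13.5.1 and 13.5.3 both say two-sided.

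**3. Where do the two rules disagree?** Inputs: n = 10, 12 or 14 (Section 6.2), and the two-period cross-over model of Section 13.5.1. Assumption: every subject has data in both periods, so the treatment comparison has n − 2 degrees of freedom. The critical values are t(0.975, n − 2) for two-sided 5% and t(0.95, n − 2) for two-sided 10%.

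| n | df | 5%: reject if abs(t) exceeds | 10%: reject if abs(t) exceeds | Ratio |
|---|---|---|---|---|
| 10 | 8 | 2.306 | 1.860 | 1.240 |
| 12 | 10 | 2.228 | 1.812 | 1.229 |
| 14 | 12 | 2.179 | 1.782 | 1.222 |

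At n = 12, any abs(t) between 1.812 and 2.228 (p between 0.05 and 0.10) is significant under Section 13.5.3, with a 90% interval that excludes zero, and not significant under Section 13.1. A 95% interval would be about 23% wider than the 90% interval (ratio 1.229).

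**4. How likely is such a result?** The chance equals the rejection probability at 10% minus that at 5%. With no effect it is 0.10 − 0.05 = 0.05.

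With an effect, power comes from the noncentral t distribution with n − 2 degrees of freedom and noncentrality d × √n. Here d is the true mean difference divided by the SD of the within-subject differences, with equal sequence sizes. The protocol gives no effect size, SD or power, so d and the 80% anchor below are assumptions.

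Anchored at 80% power under the 10% rule:

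- n = 12: noncentrality 2.674; power at 5% is 0.674; gap 0.800 − 0.674 = 0.126.
- n = 10: power at 5% is 0.667; gap 0.133.
- n = 14: power at 5% is 0.679; gap 0.121.

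Varying the assumed effect at n = 12:

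| d | Power at 5% | Power at 10% | Chance the rules disagree |
|---|---|---|---|
| 0.5 | 0.347 | 0.488 | 0.141 |
| 0.6 | 0.468 | 0.614 | 0.147 |
| 0.7 | 0.591 | 0.730 | 0.139 |
| 0.8 | 0.705 | 0.824 | 0.119 |
| 1.0 | 0.876 | 0.942 | 0.066 |

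**The case against.** The strongest reply is that the specific section overrides the general one. Sections 13.5.1 and 13.5.3 agree on 10%, they sit under the heading that holds the primary analysis, and the 5% sentence looks like leftover general wording. This makes 10% the likelier intention. It does not remove the contradiction, because Section 13.1 makes no exception and would then govern no test at all.

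A second reply is that Section 13 promises a separate SAP signed before database lock, and Section 7.7 withholds treatment allocation until lock. If that SAP fixes one level, the choice is made blind. This limits the worry about a choice made after unblinding. However, no separate SAP is among the supplied documents, so it cannot be shown to settle the level.

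A third reply concerns importance. This is a phase 1b trial with a target of 12 subjects and no sample size calculation, and its stated purpose is to inform later trials. No success or go/no-go rule in the available text depends on significance. The estimate, the 90% interval and the p-value are the same under either level; only the label changes. That is fair, and 10% may be a reasonable choice for such a trial. But the protocol does name a primary endpoint, plan hypothesis tests and set a level for them. Having done so, it needs to set one.

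Finally, any single figure for the chance of disagreement depends on an assumed effect, which is why a range is given.

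**Conclusion.** The concern holds. The current text gives two incompatible significance levels for the primary RHI test and the AI test, and any subgroup tests would inherit the same conflict. The contradiction itself rests on no assumption.

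Its size is as follows. The nominal false-positive rate per test is 5% or 10%. The chance of a result on which the sections disagree is 5% under no effect. With 12 completers it is about 7% to 15% for assumed differences of 0.5 to 1.0 SD, and 12.6% if power at the 10% level is assumed to be 80%. These figures assume complete data in both periods and equal sequence sizes. The point must be fixed because it concerns the decision threshold for the primary endpoint.

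**What to change.** State one level and its sidedness in Sections 13.1 and 13.5.3, match the interval in Section 13.5.1 to it, and carry the same wording into the SAP before database lock. There are two consistent options.

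- **Keep 10%.** Replace the 5% in Section 13.1 with a two-sided 10% level for the pharmacodynamic comparisons. Sections 13.5.1 and 13.5.3 then stand unchanged. This is the smaller edit.
- **Adopt 5%.** Change Section 13.5.3 to two-sided 5% and the interval in Section 13.5.1 to 95%, and add the sidedness to Section 13.1. At n = 12 the interval widens by about 23%, and an effect with 80% power at 10% has 67% power.

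Either way, remove the other level altogether. The cost is a few sentences and no extra data or subjects. The sponsor should check whether the change counts as a substantial amendment under Section 10.1.

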13.2 Determination of Sample Size

No formal sample size calculation has been performed for this trial. The proposed sample size is considered sufficient to provide adequate information to meet the trial objectives.

13.3 Analysis Data Sets

The Safety Set will consist of all subjects who have been randomised and received at least one dose of IMP. This analysis set will be used for safety assessments.

The PD Analysis Set (PDAS) will consist of all subjects who have been randomised and received at least one dose of IMP, provided evaluable PD variables from either Visit 2 or 3, and who have no AE or protocol deviations judged to affect the PD analysis. Individual PD values may be excluded from the analysis as specified in the SAP.

The PD Ratio Analysis Set (PDRAS) will consist of all subjects who have completed the trial up until Visit 3, provided evaluable PD variables from both Visits 2 and 3, and who have no AEs or protocol deviations judged to affect the PD analysis. Individual PD values may be excluded from the analysis as specified in the SAP.

13.4 Subject Disposition

13.4.1 Demographics and Baseline Characteristics

Descriptive statistics for demographics, weight, height, and BMI will be presented for all subjects. All data will be listed by subject.

Clinical Trial Protocol

Vicore Pharma AB Version: 2.0 Trial ID: VP-C21-013 Date: 03-MAR-2023

13.4.2 Medical/surgical history

Medical history will be presented by system-organ-class (SOC) and preferred term (PT). All data will be listed by subject.

13.4.3 Prior/concomitant medication

Prior/concomitant medications will be presented by ATC level 4 and 5. All data will be listed by subject.

13.4.4 IMP administration

All administered individual IMP administrations will be listed by subject.

13.5 Pharmacodynamic Analysis

The EndoPAT software, provided with the device, will calculate the following outcome using a computerised, automated algorithm:

- Reactive Hyperemia Index (RHI) score: post-to-pre occlusion pulse amplitude tonometry (PAT) signal ratio in the occluded arm relative to the same ratio in the control arm, and corrected for baseline vascular tone. RHI is a measure of endothelial function.
- Augmentation index (AI): calculated from PAT pulses at the baseline period. AI is a measurement of vascular stiffness.

13.5.1 Analysis of Primary Endpoint

The percentage change in the primary endpoint (RHI) will be compared between treatments using an analysis of variance model (ANOVA) adjusting for subject (random), period and treatment. The adjusted mean difference will be presented together with 90% confidence interval and associated two-sided p-value.

All data will be listed by subject.

13.5.2 Analysis of Secondary/Exploratory Endpoint

The secondary endpoint (AI) will be compared between treatments using similar ANOVA model as for the primary endpoint.

13.5.3 Statistical/Analytical Issues

All tests will be two-sided at a 10% significance level. There will be no adjustment for multiple tests.

13.5.3.1 Missing Data

There will be no imputation of pharmacodynamic or safety data.

Clinical Trial Protocol

Vicore Pharma AB Version: 2.0 Trial ID: VP-C21-013 Date: 03-MAR-2023

13.5.3.2 Examination of Subgroups

Important demographic and baseline value-defined subgroups will be examined and the results presented, *e.g.*, comparison of effects by age, sex and baseline disease severity (T2DM). A detailed description will be provided in the SAP.

13.6 Safety Analysis

13.6.1 Adverse Events

An overview of all treatment-emerging AEs including severity, relationship to IMP, SAEs and AEs leading to withdrawals of treatment and withdrawal from trial or death will be presented. The incidence of treatment-emerging AEs and SAEs will be summarised by system organ class (according to MedDRA) and preferred term (according to MedDRA) by treatment.

All treatment-emergent AEs will be listed by subject and include the verbatim term entered by the investigator.

13.6.2 Pregnancy

All pregnancy test results will be listed by subject.

13.6.3 Physical examination

Abnormal findings on the physical examination will be summarised by visit.

All physical examination data will be listed by subject.

13.6.4 Vital Signs

Vital signs data (e.g., blood pressure and body temperature) will be summarised by visit.

All vital signs data will be listed by subject.

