]	13) Abnormal laboratory value at screening indicating a potential risk for the subject if enrolled in the trial as evaluated by the investigator.	
Investigational	C21	
dosage and mode	C21 is supplied as a 50 mg capsule for oral administration. C21 200 mg (4 capsules) will be administered as a single oral dose.	
of administration	Placebo to C21	

Vicore Pharma AB
Version: 2.0
Trial ID: VP-C21-013
Date: 03-MAR-2023

	Placebo to C21 is supplied as a capsule for oral administration, manufactured as C21 without the active pharmaceutical ingredient. Placebo to C21 (4 capsules) will be administered as a single oral dose.
Criteria for Evaluation	All subjects who have received at least one dose of IMP will be included in the safety analyses. The pharmacodynamic analyses (assessed by EndoPAT) will include all treated subjects for whom the pharmacodynamic parameters can be calculated.
Statistical Analyses	All quantitative variables will be summarized by assigned treatment and time point using standard descriptive statistics. Qualitative variables will be summarized by assigned treatment and time point by means of absolute and relative frequencies.
	Percentage change in RHI will be compared between treatments using an analysis of variance model adjusting for treatment, period, and subject (random).
Sample Size Calculation	Sample size is based on what is usually seen in this type of trial and not on any statistical assumptions.
Trial Reporting	After completion of the trial, an International Council for Harmonisation (ICH) E3 guideline-compliant clinical trial report (CTR) will be prepared.

Vicore Pharma AB Version: 2.0 Trial ID: VP-C21-013 Date: 03-MAR-2023

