7.3 Treatment Assignment

Eligible subjects will be randomised to receive either C21 or placebo in a random order at Visit 2

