13.6.5 Electrocardiogram

All ECGs will be categorised as "normal", "abnormal, not clinically significant", or "abnormal, clinically significant" (as judged by the investigator). The assessment will be summarised by visit and time point relative to IMP administration.

All ECG data will be listed by subject.

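### Do the by-visit summaries of vital signs and ECG mix C21 and placebo?

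*Combined protocol and SAP*

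**What the plan says.** Three safety subsections give visit as the summary axis and do not mention treatment:

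- Section 13.6.3: "Abnormal findings on the physical examination will be summarised by visit".
- Section 13.6.4: "Vital signs data (e.g., blood pressure and body temperature) will be summarised by visit".
- Section 13.6.5, for the investigator's ECG category: "The assessment will be summarised by visit and time point relative to IMP administration".

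Two general rules supply the treatment axis. The Protocol Summary (Section 1, Statistical Analyses) says "All quantitative variables will be summarized by assigned treatment and time point using standard descriptive statistics" and "Qualitative variables will be summarized by assigned treatment and time point by means of absolute and relative frequencies". Section 13.1 says "When applicable, summary data will be presented by treatment, and by assessment time", and for listings "Individual subject data will be listed by subject number, treatment and, where applicable, by assessment time".

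On allocation, Section 7.3 says "Eligible subjects will be randomised to receive either C21 or placebo in a random order at Visit 2". The sequence ratio and any blocking are not visible. Section 13 leaves technical detail to a separate SAP, to be signed before database lock. That SAP is not part of the document under review.

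**The concern.** In a cross-over with random order, the visit number does not identify the treatment. A programmer who worked from Sections 13.6.4 and 13.6.5 alone could produce Visit 2 and Visit 3 columns that each blend C21 and placebo.

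Vital signs look the most exposed. Section 8.3.4 places them after dosing at Visits 2 and 3 and sets no pre-dose reading at those visits, so a change from pre-dose within the visit is not available. Visits 1 and 4 give off-drug readings. However, the 12-hour medication withhold (Section 5.5.2, Table 2) and the 3-hour fast (Section 5.5.1) are specified for Visits 2 and 3, so the placebo visit is the like-for-like comparator.

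Safety is part of the trial's purpose, and Section 3.4 cites vasodilation through the AT2 receptor. A modest shift in blood pressure or pulse that nobody calls clinically significant would stay out of the adverse event tables and would be diluted in a blended vital-signs table.

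**Working it through.** The plan states no figure on this point and has no formal sample size calculation (Section 13.2), so there is nothing to reproduce. The check has two parts: what a literal by-visit table would show, and whether the text calls for one.

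**1. A literal by-visit table**

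Inputs:
- N = 10 to 14 randomised subjects, target 12 (Section 6.2).
- a = number on C21 at Visit 2; b = number on C21 at Visit 3; a + b = N, assuming that all subjects complete both visits.
- m = off-drug mean, d = C21 effect, p2 and p3 = period effects.

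Expected means:
- Visit 2: m + (a/N)d + p2
- Visit 3: m + (b/N)d + p3

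Share of d carried by each visit mean. The splits are assumptions, because the ratio is not visible:

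| N | a : b | Visit 2, a/N | Visit 3, b/N |
|---|---|---|---|
| 12 | 6 : 6 | 6/12 = 50% | 6/12 = 50% |
| 12 | 7 : 5 | 7/12 = 58.3% | 5/12 = 41.7% |
| 10 | 6 : 4 | 6/10 = 60% | 4/10 = 40% |
| 14 | 8 : 6 | 8/14 = 57.1% | 6/14 = 42.9% |

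A table by treatment carries 100%. A literal by-visit table would therefore be a poor one, with roughly half of any effect in each dosing-visit column. The difference between the two visits is not a useful further measure, because the plan proposes no such comparison. Section 13.6 plans only summaries and listings for these data.

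**2. Whether the text calls for that table**

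| Source | Treatment axis | Time axis |
|---|---|---|
| Protocol Summary | Required, all variables | Time point |
| Section 13.1 | Where applicable | Assessment time |
| Section 13.6.4 | Not mentioned | Visit |
| Section 13.6.5 | Not mentioned | Visit, and time relative to dosing |

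- A table by visit alone satisfies Section 13.6.4 but breaks the Protocol Summary.
- A table by treatment alone satisfies neither the time axis of the Protocol Summary nor Section 13.6.4.
- A table of treatment by visit, with time point added for ECG, satisfies every row.

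Sections 13.6.4 and 13.6.5 thus specify the time axis and leave the treatment axis to the general rules. Visit is natural wording there, because these sections also cover Visits 1 and 4, where no study drug is given (Table 1). In a placebo-controlled cross-over, treatment is plainly applicable at Visits 2 and 3, so the qualifier in Section 13.1 does not remove it.

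**3. What protects the reader in any case**

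- Post-dose vital-sign and ECG findings judged clinically significant are reported as adverse events (Sections 8.3.4 and 8.3.5), and Section 13.6.1 tabulates those by treatment.
- All vital-sign and ECG data are listed by subject (Sections 13.6.4 and 13.6.5), and Section 13.1 puts treatment in the listings. With 10 to 14 subjects, the C21-to-placebo comparison can be rebuilt from them.
- Physical examinations at Visits 2 and 3 are symptom-driven only (Section 8.3.3), so Section 13.6.3 adds little.
- The RHI model in Section 13.5.1 contains treatment explicitly and does not depend on these tables.

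**The case for a change.** The best case for a change is that a specific section normally governs over a general one. Section 13.6.1 names treatment for adverse events, while Sections 13.6.3 to 13.6.5 name visit. A literal reader could take that contrast as deliberate and treat the qualifier in Section 13.1 as permission to leave treatment out. The placebo visit is the only like-for-like reference for post-dose blood pressure, a sub-clinical shift would not reach the adverse event tables, and a clarifying sentence would cost almost nothing.

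Part of this stands. The wording is uneven, and someone who read Section 13.6.4 in isolation could build the wrong table. The inference from Section 13.6.1 is weak, though. Adverse events are tabulated by organ class and preferred term and have no visit axis, so treatment is the natural column to name there. Nothing in Sections 13.6.3 to 13.6.5 excludes treatment, and the Protocol Summary requires it without a qualifier.

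Swapping visit for treatment at the dosing visits would also lose something, because the visit axis is what lets the reader see a period effect.

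**Conclusion.** No change to the plan is needed. The subsections leave out a word that the Protocol Summary and Section 13.1 supply, and treatment by visit is the only layout consistent with all of them. A statistician writing the SAP or the table shells would arrive at it without further instruction.

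The effect on results is nil when the plan is followed as a whole. Only under a literal by-visit reading would each dosing-visit mean carry about half of a C21 effect. That figure assumes balanced sequences and subjects who complete both visits. Even then, the loss would be confined to descriptive tables of findings not judged clinically significant, and it could be recovered from the listings.

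Two limits apply. The separate SAP, where table layout would normally be settled, was not available. The visible wording of the secondary safety objective in Section 4 is incomplete, so the safety endpoints cannot be read in full.
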